6.1 Full Analysis Set

The Full Analysis Set (FAS) includes all randomized subjects. Data will be analyzed based on subjects' randomized treatment assignment.

6.2 Safety Analysis Set

The Safety Analysis Set includes all randomized subjects who received at least 1 dose of IP. Subjects in this set will be analyzed according to the actual treatment received.

6.3 Pharmacokinetic/Pharmacodynamic Analyses Set(s)

The PK concentration analysis set will contain all subjects who received at least one dose of IP and have at least one quantifiable PK sample collected. PK concentration data will be analyzed according to the actual treatment received.

The PK parameter analysis set will contain all subjects who received at least one dose of IP and for whom at least one PK parameter can be adequately estimated. PK parameter will be analyzed according to the actual treatment received.

6.4 Interim Analysis Set(s)

Each Interim Analysis Set include all subjects randomized on or before the interim analysis cutoff date and had the opportunity to complete week 16 (actual week 16 visit date \leq the cutoff date, or randomization date + 126 - 1 $<$ cutoff date). The interim data cutoff dates are **defined as the date the last enrolled subject among those that trigger an interim analysis (Table 3-1) has** the opportunity to complete **the** week 24 visit.

7. Planned Analyses

7.1 Interim Analysis and Early Stopping Guidelines

Interim analyses (IAs) will be conducted to allow adaptation of the randomization ratio to the 3 rozibafusp alfa treatment groups, holding the allocation to placebo constant at 25%, and to assess efficacy for early futility or administrative success decisions:

- Data will be subject to ongoing checks for integrity, completeness and accuracy in accordance with the Data Management Plan with the expectation that outstanding data issues are resolved ahead of the snapshot to the extent

possible. All available data up to and including the data cut-off date will be included in the analysis based on an “as-is” snapshot of the database without data locking.

- The study team, investigators, and patients will remain blinded to the study treatment, changes in randomization allocation probabilities, and results of the interim analyses unless futility is determined.
- The first IA will be executed after the first enrolled 40 subjects are randomized and have had the opportunity to complete the week 24 assessment. Subsequent IAs will be scheduled after every additional 32 subjects are randomized and have had the opportunity to complete the week 24 assessment until full enrollment. The last IA will occur when all 320 subjects are randomized and have had the opportunity to complete the week 24 assessment. This IA will be referred to as the ‘all-subjects-week-24’ IA.
- Efficacy analyses will be performed at the IAs to assess the likelihood of rozibafusp alfa being superior to placebo by a clinically meaningful difference. From the second IA until before the last IA, if this likelihood is unacceptably low for all dose levels, the trial is recommended to stop for futility.
- Additionally, at the ‘all-subjects-week24 IA’, if this likelihood is sufficiently high in at least 1 rozibafusp alfa dose level, IA triggers an administrative success signal. This would not alter ongoing or planned activities of this study, but downstream planning for subsequent trials (e.g. a phase 3 study) may commence. Analysis planned at each IA are listed in [Table 3-1](#). **This interim analysis was cancelled due to the study being terminated for futility prior to this analysis.**

At IAs,

- For all IAs before full enrollment, the randomization ratio to each active treatment group is proportional to the posterior probability that each group has the highest response rate among the three active treatment groups with power scale of 2.

$$Allocation_d \propto \Pr \left(p_{d,52} = \max_c p_{c,52} \mid \text{Interim Data} \right), c, d \in \{\text{low, medium, high}\}$$

where $p_{d,52}$ is the posterior probability of achieving SRI-4 response for group d, calculated using a Bayesian independent logistic model with non-informative priors.

- From the second IA until before the last IA, the interim futility analysis will be performed based on the BHM as described in the primary efficacy analysis. Enrollment to the study may be stopped for futility if the posterior probability of achieving a clinically meaningful difference in SRI-4 response rates of at least 15% between each active treatment group and placebo is below 2.5% for all 3 rozibafusp alfa doses.

$$\max \Pr(p_{d,52} - p_{placebo,52} > \delta \mid \text{Interim Data}) < 0.025, d \in \{low, medium, high\}$$

where $\delta = 0.15$ and $p_{d,52}$ is the posterior probability of achieving SRI-4 response for group d, calculated using a BHM.

- The futility rule trigger is made using estimates of the response rate $p_{d,52}$ for each dose. However, due to the covariate adjustment, the Bayesian models provide estimates of $p_d \mid Z$, the response rate in each dose conditional on the stratification factor Z. The population level estimate for each dose is obtained using a weighted average of the response rate in each stratification group.

$$p_d = \sum_{Z \in Z} w_z \cdot p_d \mid Z \quad \text{for } d \in \{placebo, low, medium, high\}$$

The set Z indicates the four possible stratification combinations (hSLEDAI stratification [≥ 10 , < 10] and region [North America + Western Europe vs ROW]). The weights w_z will be set equal to the observed proportion of patients in each stratification group at the time of the analysis.

- To address the challenge of the lag time between randomization and the week 52 outcome in the adaptive design, a longitudinal model is used to impute week 52 outcome for subjects not yet complete week 52 using their week 16, week 20, or week 24 response data.

7.2 Final Analysis

The final analysis will take place after study completion is reached **or study is early terminated**, i.e. after the last subject completes last visit or early terminates from the study, and all data are collected for the study.

Data will be subject to ongoing checks for integrity, completeness and accuracy in accordance with the Data Management Plan with the expectation that all outstanding data issues are resolved ahead of the final lock. The data supporting the final analysis will be locked to prevent further changes.

8. Data Screening and Acceptance

8.1 General Principles

The objective of the data screening is to assess the quantity, quality, and statistical characteristics of the data relative to the requirements of the planned analyses.

8.2 Data Handling and Electronic Transfer of Data

The Amgen Global Study Operations-Data Management (GSO-DM) department will provide all data to be used in the planned analyses. This study will use the RAVE database. All laboratory, PK, [REDACTED] and biomarker data from the central laboratory or vendor will be transferred to GSO-DM. All efficacy and PRO data from the central vendor will be transferred to GSO-DM. All other data will be captured on the eCRF.

8.3 Handling of Missing and Incomplete Data

Subjects may have missing specific data points for a variety of reasons. In general, data may be missing due to a subject's early withdrawal from study, a missed visit, or non-evaluability of a specific clinical or laboratory measurement at its planned clinical visit.

Additionally, as the study was terminated before the planned completion, subjects may have missed clinical visits including not completing the week 52 visit. For efficacy and PRO outcomes, subjects who terminated early due to sponsor decision will be excluded from analyses of data from visits for which they did not have the opportunity to participate in by the date of study termination decision being communicated to sites, i.e. February 28, 2023. Efficacy data collected after this date will be censored and excluded from analyses for that particular visit.

Unless specified, no imputation will be used. The general procedures outlined below describe what will be done when a data point is missing.

Hybrid SLEDAI

In case of completely missing hSLEDAI assessment (e.g. missed visit) or partially missing (e.g. laboratory measurements not available), the missing post-baseline hSLEDAI items will be imputed using last observation carried forward (LOCF) if the previous analysis visit is not missing. Baseline hSLEDAI will not be carried forward to post-baseline.

The hSLEDAI total score will then be computed based on the non-missing and imputed data. **If the hSLEDAI total score cannot be evaluated after imputation, the hSLEDAI score \geq 4 points reduction from baseline will be considered not met.**

CLASI

In case of completely missing CLASI assessment (e.g. missed visit) or partially missing, the missing post-baseline CLASI items will be imputed using LOCF if the previous analysis visit is not missing. Baseline CLASI will not be carried forward to post-baseline.

The CLASI activity score will then be computed based on the non-missing and imputed data. If the CLASI activity score cannot be evaluated after imputation, the CLASI activity score \geq 50% improvement endpoint will be considered not met.

BILAG

In case of completely missing BILAG assessment (e.g. missed visit), the missing post baseline BILAG item scores will be imputed using LOCF if the previous analysis visit is not missing.

In case of partially missing, missing laboratory items (e.g. UPCR, creatinine, etc.), **nephrotic syndrome or urinary sediment** will be imputed using LOCF if the previous visit is not missing; other missing items (e.g. active nephritis, Coombs' test positive, etc.) will be imputed as 'No' or 'Not Present'.

Baseline BILAG will not be carried forward to missing post-baseline BILAG.

The BILAG organ domain scores will be based on the non-missing and imputed components. If the non-missing and imputed components are not sufficient to identify the organ domain score, worst scenario approach will be used to determine the BILAG organ domain scores.

PGA

Missing post-baseline PGA score will be imputed using LOCF if the previous analysis visit is not missing. Baseline PGA will not be carried forward to missing post-baseline PGA.

SRI-4, BICLA and LLDAS

The criteria for SRI-4, BICLA and LLDAS responses will be evaluated based on the non-missing and imputed PGA, hSLEDAI and BILAG data. If any criteria based on the non-

missing and imputed PGA, hSLEDAI and BILAG data cannot be evaluated, then the subject will be considered non-responder.

BILAG Flare index

BILAG flare index will be evaluated based on BILAG scores. In case of partially missing BILAG assessment, imputed BILAG scores will be used. In case of completely missing BILAG assessment, BILAG flare index will remain missing.

Tender and Swollen Joint Counts

If a joint is excluded (non-evaluable, missing or not done), the joint counts will be prorated based on the algorithm described below.

[figure not shown]
Prorated Joint Counts: If at least half but not all joints are evaluable (at least 14 joints for the total 28 joint count, at least 11 joints for the 22 hands and wrists joint count) then the observed prorated tender or swollen joint count will be calculated. The prorated scores will be adjusted based upon the number of evaluable joints: the counted score will be multiplied by 28 (for total) or 22 (for hands and wrists) as applicable and divided by the number of joints evaluated. If less than half of the joints are evaluable, the number of tender or swollen joints is missing. For example, if only 25 of the 28 joints are assessed at a visit and 10 of those 25 are tender and 8 of those 25 are swollen, the prorated total joint counts are:

Tender: $(10/25) * 28 = 11.20$,

Swollen: $(8/25) * 28 = 8.96$.

That is, the values of 11.20 and 8.96 will be used in calculating the % reductions in total joint counts, not the values of 10 and 8. Similar proration will be conducted for hands and wrists joint count.

If the tender and swollen joint counts cannot be evaluated after proration, the tender and swollen joint count $\geq 50\%$ improvement from baseline endpoint will be considered not met.

Dates

Missing and incomplete dates will be imputed as outlined in [Appendix E](#).

Laboratory Toxicity Grading

In cases when supplemental information for laboratory toxicity grading is missing or the result is ambiguous, the worse toxicity grade possible will be assigned.

Laboratory Measurements

Laboratory measurements that are below the lower quantification limits will be considered equal to the lower limit of quantification for all analyses unless explicitly noted otherwise.

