8.2.1 Reasons for Removal From Study

Reasons for removal of a subject from the study are:

- Decision by sponsor
- Withdrawal of consent from study
- Death
- Lost to follow-up

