3.1 Study Design

This is a Bayesian adaptive phase 2b, multi-center, double-blind, randomized, placebo controlled, 52-week, dose-ranging study in subjects with active SLE and inadequate response to SOC therapies including OCS, immunosuppressants, and immunomodulators. Subjects will be randomized to receive either placebo or 1 of 3 doses of rozibafusp alfa with the last dose at week 50. Study duration for a single subject will be 52 weeks plus the screening period and safety follow-up period.

Treatment will be administered every 2 weeks (Q2W). Subjects are required to attend as many follow-up visits as necessary to ensure a minimum of 16 weeks of safety follow-up after the last administration of the investigational product. Tapering of OCS from the baseline dose will be allowed from week 24 through week 44. The first interim analysis (IA) will be executed after the first 40 enrolled subjects have had the opportunity to complete the week 24 assessment. Additional IAs may be executed after approximately every 32 newly enrolled subjects have had the opportunity to complete the week 24 assessment. The last IA will occur when all 320 subjects are randomized and have had the opportunity to complete the week 24 assessment. This IA will be referred to as the 'all-subjects-week-24 IA'. The purpose and analyses planned at each IA are listed in [Table 3-1](#).

Based on the Data Monitoring Committee's recommendation following review of the results from the 6th IA and subsequent decision by the Data Access Plan Team, the study was terminated due to futility and further enrollment in the study was stopped. Previously enrolled subjects were discontinued from IP and terminated the study after being followed for an additional 16 weeks following last dose of IP. The remaining planned IAs, including the last IA ('all-subjects-week-24-IA') and the primary analysis, were not conducted.

Table 3-1. Planned Analyses Schedule: Decisions at each Interim Analysis, Primary Analysis, and Final Analysis

Time point	Adaptive Decision	Number of subjects with opportunity to complete week 24
1 st IA	RAR	40
2 nd IA	Futility, RAR	72
3 rd IA	Futility, RAR	104

4 th IA	Futility, RAR	136
5 th IA	Futility, RAR	168
6 th IA	Futility, RAR	200
7 th IA ^{ac}	Futility, RAR	232
Last IA ^{bc}	Administrative Success	320
Primary Analysis ^c	Not applicable	All subjects have had the opportunity to complete week 52
Final Analysis	Not applicable	All subjects reach EOS

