5.3 Study Dates

End of 52-Week Treatment Period Date

End of 52-week treatment period date for each subject is defined as the date of the last assessment for the week 52 visit, the end of study date in case of **subject** early termination, study day 394, or **February 28, 2023 (end of study date due to early termination decision)**, whichever occurs first.

Start of Safety Follow-up Period Date

Start of safety follow-up period date for each subject is defined as the end of 52-week treatment period date plus one day.

End of Study Date

End of study for each subject is the date recorded on the End of Study CRF page.

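### The unreachable-visit exclusion in SAP 8.3 depends on exit reason, so equally late subjects who withdrew, died or were lost stay in the week-52 denominator, nearly all as non-responders under one-step LOCF

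*SAP*

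**What the plan says.** SAP 8.3 first describes ordinary missingness (withdrawal, missed visits, non-evaluable measurements), then missingness caused by the early stop. For the second kind, "subjects who terminated early due to sponsor decision will be excluded from analyses of data from visits for which they did not have" the chance to attend by 28 February 2023, when sites were told of the decision. Efficacy data collected after that date are also dropped.

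The other provisions that matter are:

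- **Exit routes.** Protocol 8.2.1, under "Reasons for removal of a subject from the study are", lists sponsor decision, withdrawal of consent, death and loss to follow-up. The SAP 8.3 exclusion covers only the first.
- **Analysis set.** SAP 6.1: "The Full Analysis Set (FAS) includes all randomized subjects". SAP 9.5 makes this the default efficacy set.
- **Carry-forward.** Missing post-baseline hSLEDAI items are "imputed using last observation carried forward (LOCF) if the previous analysis visit is not missing". CLASI, wholly missing BILAG and PGA carry the same condition. Baseline is never carried forward.
- **Composites.** For SRI-4, BICLA and LLDAS, if any criterion based on non-"missing and imputed PGA, hSLEDAI and BILAG data cannot be evaluated, then the subject will be considered non-responder".
- **Joint counts.** "If the tender and swollen joint counts cannot be evaluated after proration, the tender and swollen joint count" endpoint of at least 50% improvement is scored as not met. Proration is specified; LOCF is not.
- **Conduct after the stop.** SAP 3.1: "Previously enrolled subjects were discontinued from IP and terminated the study after being followed for an additional 16 weeks following last dose of IP". With SAP 5.3, I read this to mean that everyone still on study on 28 February 2023 was ended by the sponsor. Exits after that date are not part of this point.

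**The concern.** Take two subjects randomized in September 2022. Neither could have reached week 52 by 28 February 2023. The one still on study that day is excluded at week 52. The one who withdrew consent in December 2022 is retained, has no week-48 visit to carry forward, and is scored a non-responder.

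Non-responder imputation is defensible when the whole cohort is in the denominator. Here the late cohort's stayers are removed and its leavers kept, so it contributes almost only failures. The week-52 rate is pulled down in any arm that has both such leavers and responders. The side-by-side arm summary is distorted if their share differs by arm, through differential drop-out or because response-adaptive randomization (SAP 3.3 and 7.1) gives the active doses different shares of late subjects.

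The affected endpoints are SRI-4, BICLA, LLDAS, CLASI 50% and joint-count 50%. Flare rates use exposure time, and PRO scores have no imputation for missed visits, so neither is affected.

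**Working it through.** The plan gives no figure on this point to reproduce. From the documents come the 28 February 2023 cutoff, week-52 target day 365 (Appendix D), 200 subjects with week-24 opportunity at the sixth interim analysis (Table 3-1), and the 40% placebo rate (SAP 3.2). Accrual, lag and drop-out are my assumptions.

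**Who is late.** Day 365 falls on or before 28 February 2023 only if study day 1 was by 28 Feb 2023 − 364 days = 1 Mar 2022.

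**Simplest form.** With n opportunity subjects in an arm and a 40% rate, the first retained late leaver lowers the rate by 40/(n+1) points: 40/46 = 0.9 at n = 45 and 40/36 = 1.1 at n = 35.

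**Scenario model.** Let *a* be accrual per week, continuing to 28 February 2023, with 8 weeks from the sixth interim cutoff to that date.

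- Randomized: N = 200 + (24+8)a = 232, 264, 296 for a = 1, 2, 3.
- Late share: m = 52a/N = 22%, 39%, 53%. Opportunity subjects: 180, 160, 140 (45, 40, 35 per arm if equal).
- Share of late subjects who left for a non-sponsor reason, with annual drop-out r, h = −ln(1−r), and follow-up uniform over 0-52 weeks: d = 1 − (1−e^−h)/h = 5.1% (r = 10%) or 10.4% (r = 20%).
- Share of late subjects who left after a week-48 visit: g = 0.03-0.05%, about 0.5% of leavers. A simulation agrees: 99.4-99.5% of late leavers have no week-48 or later visit. This is 98.8-98.9% if an early-termination visit falls on the day of leaving, and 97.0-98.3% if opportunity is judged at day 394.

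One-step LOCF: rate = [0.40(1−m) + 0.40·m·g] / [(1−m) + m·d].

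| Accrual per week | Late leavers per arm (r = 10% / 20%) | A 40% rate reads |
|---|---|---|
| 1 | 0.7 / 1.3 | 39.4% / 38.8% |
| 2 | 1.3 / 2.7 | 38.7% / 37.5% |
| 3 | 2.0 / 4.0 | 37.9% / 35.9% |

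Worked cell (a = 2, r = 20%): 0.2425 / (0.6061 + 0.3939 × 0.1037) = 0.2425 / 0.6469 = 37.5%. A lag of 4 or 12 weeks instead of 8 gives 38.7/37.4% or 38.8/37.6%. The joint-count endpoint (no LOCF, same 40%) also gives 38.7/37.5%. At week 24 the shift is 0.2-0.4 points.

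**Chained LOCF.** If an imputed visit counts as not missing, the c = 84-85% of leavers who left after week 4 carry a value. With a fraction q of those being responders, rate = [0.40(1−m) + q·c·m·d] / [(1−m) + m·d]. At a = 2 this gives 39.3-38.5% (q = 20%), 39.8-39.6% (q = 40%) and 40.3-40.7% (q = 60%). The shift reverses above q = 0.40/c, about 47%.

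**Between-arm distortion** (one-step LOCF, equal true rates of 40%):

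- d = 5% versus 10% at m = 40%: 38.7 − 37.5 = 1.2 points.
- m = 40% versus 50% at d = 10%: 37.5 − 36.4 = 1.1 points.
- Extreme, m = 25% versus 50% at d = 10%: 38.7 − 36.4 = 2.3 points.

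**Yardstick.** At n = 40 the standard error is √(0.24/40) = 7.7 points for one arm and 11.0 for a difference.

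**The case against.** The strongest defence is that SAP 8.3 sorts missing data by cause. A subject who withdrew in December 2022 misses week 52 because of the withdrawal, not the termination. Scoring ordinary withdrawals as failures keeps to the all-randomized population of the estimand, and no other passage contradicts the rule. This does not rescue it. The exclusion turns on whether a visit could be reached by 28 February 2023. That is a calendar fact, which the exit reason does not change, and failure imputation is coherent only if the equally late stayers are also counted.

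The points on weight largely stand. SAP section 10 removes treatment comparisons, and futility had already been decided at the sixth interim analysis. The documents give no actual sample size, accrual, lag, drop-out rate or date of last enrolment, so such subjects may be few or none. Under chained LOCF the direction is not fixed. The SAP does not say whether LOCF chains, but the denominator depends on exit reason under either reading, and the joint-count endpoint does not involve LOCF.

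SAP 8.4 and 9.2 tabulate withdrawals and reasons, which lets a reader see differential exit by arm but does not correct a visit denominator. A calendar cut also discards some observed week-52 visits. That cost is real and is counted in the fix.

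**Conclusion.** The concern holds, at minor severity. On the plain text, whether a subject who could not have reached week 52 enters the week-52 responder denominator depends on why the subject left. Under one-step LOCF, and for joint counts under any reading, nearly all of those kept count as failures. In the central case (2 per week, 8-week lag, 10-20% annual non-sponsor drop-out) a 40% rate is reported as 38.7-37.5%. The 35.9% figure stacks the fastest accrual on the highest drop-out. These figures illustrate the size under stated assumptions; they are not estimates of bias in this trial. The shift is well inside sampling error, but the arm-by-arm percentages are the efficacy result that will be reported.

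**What to change.** In SAP 8.3, define each visit's set for the responder endpoints by calendar opportunity alone, whatever the exit reason. Include a subject from the Full Analysis Set at a visit only if the scheduled date (study day 1 + target day − 1, so + 364 days for week 52) plus the protocol window of 3 business days is on or before 28 February 2023. Apply this one cut to attenders and non-attenders alike. It is date-based like SAP 6.4, but without that section's branch on actual visit date, which would admit attenders only. Apply LOCF and non-responder imputation only inside the set. State whether LOCF is one-step or chained. Report numbers included and excluded by visit and arm beside the exit reasons already planned in SAP 9.2.

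The cost is one SAP sentence and one date-derived flag, with no new data. At 2 per week the week-52 denominator becomes 264 − 2 × (367 to 369)/7, about 159, instead of 165-171 (160 plus 5.3-10.8 late leavers). The cut loses at most 2 × (6 to 10)/7 = 1.7-2.9 subjects who attended early within the protocol window, or 2 × 19/7 = 5.4 if attendance from Appendix D day 351 counts.

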Systemic Lupus Erythematosus Responder Index (SRI-4)

A subject achieves SRI-4 response if all of the following criteria are met:

1. ≥ 4 -point reduction from baseline in hSLEDAI score
2. no new BILAG 2004 A and no > 1 new BILAG 2004 B domain scores compared with baseline (e.g. no B, C, D or E scores at baseline becomes A or no more than 1 C, D or E score at baseline becomes B)
3. and < 0.3 -point deterioration from baseline in PGA (scale 0 to 3).
4. no use of more than protocol-allowed therapies (i.e. initiation or increase from baseline in oral corticosteroid (OCS) dose > 5 mg/day (prednisone or equivalent) or intravenous (IV) or intramuscular (IM) at any time point during the study; initiation or increase in OCS dose ≤ 5 mg/day (prednisone or equivalent) after week 10; initiation or increase in OCS dose ≤ 5 mg/day (prednisone or equivalent) between week 0 and week 8 that was not returned to baseline dose within the following 2 weeks; initiation or increase from baseline of immunosuppressant/immunomodulator(s) at any time during the study.)

The latest visit date among hSLEDAI, BILAG and PGA will be considered the SRI-4 visit date. In the case when all three visit dates are missing, the upper limit of the analytic window of this visit will be the SRI-4 visit date.

BILAG-based Composite Lupus Assessment (BICLA)

A subject achieves BICLA response if all of the following criteria are met:

1. at least one gradation of improvement in baseline BILAG domain scores in all body systems with moderate or severe disease activity at entry (e.g., all A (severe disease) domain scores at baseline falling to B (moderate), C (mild), or D (no activity), and all B domain scores at baseline falling to C or D)
2. no new BILAG 2004 A domain score and no > 1 new BILAG 2004 B domain scores compared with baseline
3. no worsening of the hSLEDAI score from baseline
4. < 0.3-point deterioration from baseline in PGA (scale 0 to 3)

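### SAP 8.3 carries assessments forward one visit without asking whether the subject was still in the study, so a week-48 responder who then dies or leaves can be reported as a week-52 SRI-4 responder

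*SAP*

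**What the plan says.** The opening of SAP 8.3 gives the causes of missingness that the section covers: "data may be missing due to a subject's early withdrawal from study, a missed visit, or non-evaluability". Study withdrawal therefore stands beside the ordinary missed visit.

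The component rules follow:

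- hSLEDAI: "the missing post-baseline hSLEDAI items will be imputed using last observation carried forward (LOCF) if the previous analysis visit is not missing".
- BILAG, when the whole assessment is missing: "the missing post baseline BILAG item scores will be imputed using LOCF if the previous analysis visit is not missing".
- PGA: "Missing post-baseline PGA score will be imputed using LOCF if the previous analysis visit is not missing".
- CLASI has the same rule. For all four, baseline is not carried forward.

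The composites are then built on the filled data: "The criteria for SRI-4, BICLA and LLDAS responses will be evaluated based on the non-missing and imputed PGA, hSLEDAI and BILAG data". The non-responder rule is a fallback. It applies only when a criterion, after imputation, "cannot be evaluated, then the subject will be considered non-responder".

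SAP 5.6 also dates an SRI-4 for which no component visit took place: "when all three visit dates are missing, the upper limit of the analytic window of this visit will be the SRI-4 visit date".

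The only exclusion tied to study status is in SAP 8.3. It covers subjects ended by sponsor decision who had no opportunity for the visit by 28 February 2023. The primary estimand (SAP 2.1) addresses discontinuation of investigational product and use of more than the allowed therapies. It does not name death or withdrawal from the study. The Full Analysis Set (SAP 6.1) keeps every randomized subject.

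**The concern.** The primary endpoint is response at week 52 among all randomized subjects. A subject who died before week 52 cannot be in response then, and the status of one who withdrew is not known. Because the carry-forward rule is triggered only by the existence of the previous analysis visit, it treats both like a subject who skipped one appointment. Once all components are filled, SRI-4 can be evaluated and the non-responder fallback is never reached.

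The fourth SRI-4 criterion offers little protection. Under Protocol 8.2, data are included up to withdrawal of consent (publicly available data aside), so rescue therapy started afterwards would normally not be seen and the criterion passes by default.

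The same rule reaches SRI-4 at week 24 (carried from week 20), BICLA, LLDAS and the CLASI 50% endpoint. At stake is the accuracy of the responder counts by arm, which are the primary result in the final report. Table 9-1 plans one sensitivity analysis, on investigator versus adjudicated data, and it would not reveal carried-forward responders.

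**Working it through.** The plan states no figure for this effect, so there is none to reproduce. The check is a trace of the rule, followed by a size under stated assumptions.

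**Trace.** Efficacy windows in SAP Appendix D: week 48 is days 323-350 (target day 337) and week 52 is days 351-394 (target day 365). In every case no excess therapy is recorded unless stated.

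| Subject | SAP as written | Carry-forward limited to subjects still in study |
|---|---|---|
| Full week-48 response, dies or withdraws, nothing on days 351-394 | Responder | Non-responder |
| Full week-48 response, still in study, misses week 52 only | Responder | Responder |
| Leaves before any week-48 assessment | Non-responder | Non-responder |
| As the first row, but excess therapy recorded before exit | Non-responder | Non-responder |

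Only the first row changes. Examples are a death on day 350 after a week-48 visit on day 337, or a last visit on day 330, which itself supplies the week-48 value.

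Three conditions bound the case:

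1. All components must be available at week 48.
2. There must be no assessment on days 351-394, since an exit visit in that window counts as observed week-52 data.
3. The subject must not fall under the sponsor-termination exclusion.

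The trace carries one visit only. The SAP does not say whether an already imputed visit counts as not missing; if it did, the problem would be wider.

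**Size.** Assumptions, none of them from the documents: 15-25% of subjects leave the study, evenly over 52 weeks, and 40-65% of them were responding at their last visit. The 40% and 65% echo the planned placebo rate and that rate plus 25 points (SAP 3.2).

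- Four-week intervals: 52 / 4 = 13.
- Exits per interval: 0.15 / 13 = 1.15% and 0.25 / 13 = 1.92% of an arm.
- Carried-forward responders: 1.15% × 0.40 = 0.46 points and 1.92% × 0.65 = 1.25 points, so roughly 0.5-1.2 points per arm.
- At the planned 320 / 4 = 80 per arm: 80 × 0.0046 = 0.4 subject and 80 × 0.0125 = 1.0 subject.
- Weight of one such subject: 1 / 80 = 1.25 points. Enrolment stopped early, so arms may be smaller; at an assumed 50 per arm it is 1 / 50 = 2.0 points.

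**Between arms.** Take a 25-point difference under the SAP rule and suppose the share of such subjects differs by 2 points. Reclassifying them gives 25 - 2 = 23 points if the share is higher on active and 25 + 2 = 27 points if it is higher on placebo. Equal shares leave it at 25.

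**The case against.** The strongest reply is about consequence. The primary analysis was cancelled (SAP Table 3-1), statistical comparisons between groups were removed (SAP 10), and Table 9-1 asks only for a number and percentage by arm. No test in the final analysis depends on this rule. That stands and limits the weight of the point.

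The size may also be generous. People about to leave may respond less often than 40-65%. Subjects who stop investigational product are encouraged to keep attending efficacy visits (Protocol 5.1 and 8.1), and exit visits on days 351-394 are used as observed. That stands too.

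A reader might infer that the rule always inflates response and favours the active arms. The documents do not support this. The rate is higher only relative to non-responder imputation. For a withdrawn subject the true week-52 status is unknown, and the rule equally holds week-48 non-responders as non-responders. No differential exit is shown.

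A reader might also cite the joint-count endpoint, which has no carry-forward and scores the same subject as not met. That contrast arises for any missed visit and would remain after the fix, so it is not evidence for this point.

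Finally, the hSLEDAI paragraph illustrates missingness with a missed visit and unavailable laboratory results, not with withdrawal, and SAP 8.3 says that nothing is imputed unless specified. One could read withdrawal as outside the rule. But those are examples, the section names withdrawal as a cause at the outset, and SAP 5.6 expects an SRI-4 without any visit. No text in either document makes death or study withdrawal non-response. This reading does not remove the problem, though it shows that clarification is needed.

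**Conclusion.** The point holds, at modest size. SAP 8.3 gives a stated rule under which a week-48 responder who dies or leaves, with nothing recorded on days 351-394, is reported as a week-52 responder. The result is certainly wrong for deaths and unsupported by data for withdrawals and losses to follow-up. Since the written estimand assigns no strategy to study withdrawal, the rule does not contradict it for those subjects; the handling is simply not stated there.

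The expected effect is about 0.5-1.2 points per arm, resting on the assumed 15-25% exit spread evenly and 40-65% responding at the last visit. The direction of the between-arm effect is not known. Reported response rates change and no hypothesis test does. It would be wrong to infer that the trial's conclusion is in doubt: the documents give no exit counts from which any such effect could be shown. The change is still worth making because it is simple and the affected counts are the primary reported result.

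**What to change.** In SAP 8.3, for hSLEDAI, BILAG, PGA and CLASI:

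- When an assessment is completely missing, apply LOCF only if the subject was still in the study at that visit, meaning an end-of-study date on or after the visit's target day (day 365 for week 52, day 169 for week 24).
- Count subjects who died, withdrew consent or were lost to follow-up before that day, with no assessment in the visit window, as non-responders.
- Keep item-level LOCF for partially missing data at attended visits. Otherwise a subject seen on day 355 with one laboratory item missing would wrongly become a non-responder.
- Keep the sponsor-termination exclusion as it is.

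State this handling of death and withdrawal alongside the estimand in SAP 2.1, so that it does not enter only through a missing-data rule. Report the number of responders by LOCF in each arm.

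The cost is a short addition to SAP 8.3, a matching statement in SAP 2.1, one condition in the derivation program and one added count. Response rates may fall slightly. SAP 7.1 keeps the blind only unless futility is determined, and it was, so the change should be documented as made after the futility decision.
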